#### **3.2 SECONDARY OBJECTIVES**

There are four secondary objectives.

- To compare observed RFSs for the study population with the predicted RFSs for the study population. The predicted RFS values will be calculated from each patient's clinical and pathologic data by standard algorithms (Duke and CaPSURE). The observed and predicted RFSs will be presented as Kaplan-Meier plots and comparisons will be performed using the logrank test.
- To compare the observed RFS with the RFSs of a historical comparison group of MUSC prostatectomy patients. These patients will be matched to the experimental group for race, Gleason score, and pathological stage. The observed, historical RFSs will be presented as Kaplan-Meier plots and comparisons will be performed using the logrank test.
- To describe associations between the RFS values and various immunologic, genetic, and biochemical parameters on research blood and tissue specimens.
- To describe the toxicity of PROSTVAC-V/F in this patient population.

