#### 4.3 INCLUSION CRITERIA

1. Age  $\geq 21$
2. Completed radical prostatectomy for pathologically-verified adenocarcinoma of the prostate no more than 120 days prior to start of treatment. The following procedures are acceptable: radical retropubic prostatectomy (RRP), laparoscopic radical prostatectomy (with or without robotic assistance; LAPD), radical perineal prostatectomy (RPP).
3. Post-operative PSA  $< 0.2$  ng/mL by 120 days after prostatectomy
4. Must have one or more of the following:
  - pT3b or pT4 primary tumor
  - Gleason score 8-10
  - pN1 lymph node disease
  - positive surgical margins
  - pre-operative PSA of  $\geq 10$  ng/mL
  - presence of any tertiary Gleason 5 component on the prostatectomy pathology report.

**Note:** Patients with pT3a disease who lack one of the above criteria, and who refuse adjuvant radiation, may also be enrolled.

5. ECOG performance status 0-1
6. Adequate hematologic, renal, liver function per parameters in Table 1
7. Subject of fathering potential must agree to use an adequate method of contraception to avoid conception throughout the study and for at least 4 weeks after the last dose of study drug to minimize the risk of pregnancy.
8. Subjects must have had a negative bone scan, and CT of abdomen and pelvis within 26 weeks prior to registration. Additional forms of imaging (Prostascint scan, MRI) may be substituted for a CT scan of the abdomen and pelvis if clinically indicated.

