**Sample Size Justification:** To estimate the likelihood of RFS at 2 years for subjects at high risk of relapse, we extracted data from two sources. The first source is a database of high risk subjects that we have previously used in published research (122). The database contains clinical synopses of 243 subjects treated with radical prostatectomy (retropubic, laparoscopic, and perineal) for high-risk prostate cancer. These subjects were treated by multiple surgeons at several academic medical centers. None received any adjuvant therapy. High-risk features included one or more of the following criteria: pre-operative PSA  $\geq$  10 ng/mL; Gleason score 8-10; positive surgical margins, seminal vesicles, extraprostatic extension, or lymph nodes; persistently detectable PSA  $>45$  days after surgery. Relapse-free survival was defined as the interval (days) from prostatectomy to the first of the following: a) PSA of  $\geq$  0.2 ng/mL (confirmed)

>30 days later, b) appearance of lesions consistent with metastases on imaging studies, or c) institution of new prostate cancer therapy. The observed 1yr probability of RFS was 0.751 and the 2yr probability of RFS was 0.645.

An additional source of data for RFS was the ECOG E3886 study (13), in which subjects with node-positive prostate cancer after radical prostatectomy (n = 98) were randomized to immediate ADT, or ADT at the time of clinical relapse. This analysis was performed by [name] (ECOG statistical office) at our request, in 2010. Relapse was defined as the first of the following: a) the appearance of local or distant metastases identified by imaging or physical examination, b) the first increase in PSA  $> 0.1$  ng/mL following a post-prostatectomy PSA nadir of  $< 0.1$  ng/mL or c) death from any cause. The RFS probability curve is shown in Appendix B. The observed 1yr probability of RFS was 0.73 and the 2yr probability of RFS was 0.56.

While the two groups differ somewhat in the disease status of the subjects, as well as frequency and manner of follow up, the probabilities of RFS agree quite closely. For the purposes of our power analysis and sample size, we will assume that the true probability of RFS at 2 years, for patients similar to our proposed study population, is 0.60.

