We define an “interesting” reduction in the risk of relapse to be 30% (i.e., increase in the probability of RFS from 0.6 to 0.78). Assuming a one-sided alpha = 0.1, with 30 evaluable patients, we have 80% power to detect this difference based on an exact binomial test. Thus if among 30 evaluable subjects, at least 24 are recurrence free at 24 months, we will reject the null hypothesis (2 year RFS=0.60) and conclude that the PROSTVAC intervention improves RFS relative to the current standard of care in this patient population (one-sided p-value  $\leq 0.025$ ). Anticipating a final sample size of 30 patients with 10% drop out rate, we plan to enroll 33 patients for this study.

**Interim Analysis:** An interim analysis for futility will be performed through Simon’s minimax two-stage design (Simon, 1989) when a total number of 19 patients are evaluable. The design is described as follows:

**Stopping criteria:** Stop the study if there are 11 or fewer recurrence free among the first 19 evaluable patients. Otherwise, additional patients will be accrued resulting in a total evaluable sample size of 30.

**Decision rule at N=30 evaluable patients:** Reject the null hypothesis if there are 22 or more recurrence free among the 30 evaluable patients. We claim that the PROSTVAC intervention improves RFS relative to the current standard of care in this patient population. This design controls the type I error rate at 0.1 and yields the power of 0.8.

**Safety Monitoring:** Continuous safety monitoring will be performed with early stopping rules in the case of unacceptable risk to the subjects, defined as evidence in favor of a risk of a grade 3 or greater toxicity deemed to be possibly related to treated of 25% vs. an acceptable rate of 10%. Stopping criteria are shown in the table below. The stopping rules are based on a likelihood ratio. Specifically, the likelihood ratio is calculated based on a hypothesized 10% event rate (safe) vs, a 25% event rate (unsafe) and likelihood ratios in excess of 8 (in favor of an event rate of 25%)

are considered sufficient evidence to stop the trial. For example, 7 events in 33 patients yields an event rate of 0.21, which has a likelihood ratio of 9.21 favoring a rate of 25% vs. 10%.

Stop if:	Likelihood Ratio	Observed Event Rate
3 events in $\leq 6$ patients	$\geq 9.04$	$\geq 0.50$
4 events in $\leq 12$ patients	$\geq 9.08$	$\geq 0.33$
5 events in $\leq 18$ patients	$\geq 9.13$	$\geq 0.28$

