## Key Eligibility Criteria

A total of 20 patients were enrolled in [name] study, and all of them had one or more high risk features for early relapse. High risk features included 1) pT3 or pT4 primary prostate cancer, or 2) one or more lymph nodes containing metastatic prostate cancer, or 3) detectable PSA ( $\geq 0.2$  ng/mL) after prostatectomy, or 4) an 84-month risk of relapse  $>40\%$  by the 1999 ~~Kattan nomogram~~.

In E3886, one hundred patients were randomized to either immediate androgen deprivation therapy (ADT) or deferred ADT. Two patients were ineligible due to no prior radical prostatectomy and no lymphadenectomy, resulting in 47 immediate ADT and 51 deferred ADT patients eligible for follow-up. To find a similar cohort from E3886 to evaluate PFS, the 98 eligible patients were evaluated for the high risk features listed above, and Table 1 shows the risk features in these patients. Ten (10%) patients had pT3a prostate cancer and 46 (47%) had pT3b disease. Due to limited information collected on this study, we were not able to determine whether a patient had pT4 disease or not. All patients had at least one positive node. Seventeen patients (17%) had detectable PSA after prostatectomy. The 84-month risk of relapse by the 1999 ~~Kattan nomogram~~ was not assessed for these patients. Based on the information above, all E3886 eligible patients ( $n=98$ ) had one or more high risk features and were included in the analysis.

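### The 0.60 null is probably too low for men this trial can enrol, and the 22-of-30 success rule has almost no slack to absorb that

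*Combined protocol and SAP*

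**What the plan says.** The Sample Size Justification in section 10.1 draws the null from two series.

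- **Database, n = 243.** Nobody received adjuvant therapy. The list of high-risk features that qualify a man includes "extraprostatic extension, or lymph nodes; persistently detectable PSA" more than 45 days after surgery. RFS runs from prostatectomy; the events are confirmed PSA of at least 0.2, metastases on imaging, or new therapy. Stated RFS is 0.751 at 1 year and 0.645 at 2 years.
- **E3886.** Section 10.1 describes "subjects with node-positive prostate cancer after radical prostatectomy (n = 98) were randomized to immediate ADT, or ADT at the time of clinical relapse". The PSA trigger is above 0.1. Stated RFS is 0.73 and 0.56, with no arm named. Appendix B recalculates PFS from surgery and reports "Seventeen patients (17%) had detectable PSA after prostatectomy" (8 of 47 immediate ADT, 9 of 51 deferred).

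The section concedes some difference in disease status, makes no adjustment, and concludes: "we will assume that the true probability of RFS at 2 years, for patients similar to our proposed study population, is 0.60".

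The trial's own entry rule (section 4.3) is PSA below 0.2 "ng/mL by 120 days after prostatectomy". Appendix A, note m, requires a repeat before Day 1 if that result is more than 30 days old. Treatment starts within 120 days of surgery (section 5.1), and section 7.5 counts RFS from surgery.

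Section 10.1 gives two success rules for the same 30 men: at least 24 recurrence-free, and, under the Simon minimax design, at least 22 after a futility stop at 11 or fewer of 19.

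**The concern.** In a single-arm trial the null value is the control group. Here the controls and the trial men start the same clock at surgery, but only the trial men must be free of PSA failure some weeks or months later. A man who fails before that point counts against the controls and cannot enter the trial. A database man with persistent PSA of 0.2 or more meets that series' relapse definition almost at once, yet would be ineligible here.

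E3886 has two further features that depress its RFS relative to this trial: every man is node-positive, and the PSA trigger is lower. The trial also admits men on positive margins, pre-operative PSA or a tertiary Gleason 5 component alone.

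If eligible untreated men already do better than 0.60, an inactive vaccine would be declared effective more often than the stated 10%. The secondary MUSC comparison has the same gap: "These patients will be matched to the experimental group for race, Gleason score, and pathological stage", but not for post-operative PSA or event-free status at entry.

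**Working it through.** **1. Reproduce the plan's design** ("increase in the probability of RFS from 0.6 to 0.78"). For the Simon rule, the probability of success is the sum over x = 12 to 19 of P(X1 = x) × P(X2 ≥ 22 − x), with X1 ~ Bin(19, p) and X2 ~ Bin(11, p).

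- At p = 0.60: 0.093. At p = 0.78: 0.801. The stated 0.1 and 0.8 reproduce.
- For at least 24 of 30: 0.017 at 0.60, which agrees with the stated p ≤ 0.025, but power at 0.78 is 0.499, not 0.80. The futility look does not alter this rule, since a man-count of 11 or fewer at stage 1 can reach at most 11 + 11 = 22.

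**2. Where 0.60 comes from.** The simple mean is (0.645 + 0.56)/2 = 0.6025. Weighting by size gives (243 × 0.645 + 98 × 0.56)/341 = 0.621.

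**3. Condition on being event-free at entry.** Use S(2 years)/S(entry), with S(entry) = S(1 year)^(d/365). Constant hazard in year 1 is my assumption.

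| Entry day d | Database | E3886 | Mean |
|---|---|---|---|
| 60 | 0.645/0.954 = 0.676 | 0.56/0.950 = 0.590 | 0.633 |
| 120 | 0.645/0.910 = 0.709 | 0.56/0.902 = 0.621 | 0.665 |

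**4. Allow for a later reading of status.** Appendix A schedules the last visit at Day 730 on study, while section 7.5 says two years after surgery. If status is read at Day 730 on study, follow-up runs d days longer. Multiply each value by its year-2 survival ratio to the power d/365, assuming that hazard continues (0.645/0.751 = 0.859 for the database; 0.56/0.73 = 0.767 for E3886). The means become (0.659 + 0.565)/2 = 0.612 at d = 60 and (0.674 + 0.569)/2 = 0.622 at d = 120.

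**5. Type I error if the true untreated RFS is not 0.60.**

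| True untreated RFS | Simon, ≥22/30 | ≥24/30 |
|---|---|---|
| 0.60 (plan) | 0.093 | 0.017 |
| 0.612 (step 4, d = 60) | 0.117 | 0.024 |
| 0.622 (step 4, d = 120) | 0.14 | 0.030 |
| 0.633 (step 3, d = 60) | 0.17 | 0.040 |
| 0.645 (database as stated) | 0.207 | 0.052 |
| 0.665 (step 3, d = 120) | 0.28 | 0.081 |

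The error passes 0.10 at about 0.604 under the first rule and at about 0.675 under the second.

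**6. Which E3886 arm is 0.56?** Appendix B gives 5-year PFS of 83% (immediate ADT, n = 47) and 27% (deferred, n = 51). If 0.56 pooled all 98, the immediate arm would be at least 0.83 at 2 years, so the deferred arm would be at most (0.56 × 98 − 0.83 × 47)/51 = 0.31. That is implausibly close to its 0.27 at 5 years. A constant hazard to 0.27 at 5 years gives 0.27^(1/5) = 0.77 and 0.27^(2/5) = 0.59, near the stated 0.73 and 0.56. So 0.56 fits the deferred arm alone. With the deferred arm at 0.56, pooling would give at least (0.83 × 47 + 0.56 × 51)/98 = 0.69.

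**The case against.** Several arguments go the other way.

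- **Immediate ADT.** A reader might infer that ADT-treated men in E3886 are another reason that 0.60 is too low. The documents point the opposite way: ADT men relapse less, so including them would raise the null, and step 6 suggests they are not in the 0.56 at all. What stands is a labelling gap, because section 10.1 cites 98 men and names no arm.
- **Detectable PSA in E3886.** A reader might remove the 17 men and quote 0.56 × 98/81 = 0.68. That assumes all 17 had failed by 2 years. Section 10.1 defines PSA relapse there as a rise after a nadir below 0.1, which men who never reached that nadir could not meet. If none had failed, the figure would be (0.56 × 98 − 17)/81 = 0.47. For this source, even the direction of that correction is open.
- **The 24-of-30 rule.** Under it the error stays below 0.10 across the whole 0.633 to 0.665 range. This is correct, but the rule does not have the 80% power claimed for it; the 22-of-30 rule is the one that reproduces the stated design.
- **Offsets.** Death is a trial event but not a database event, which makes the null slightly too high. A later reading of status shrinks the gap, as step 4 shows. End-of-study scans are scheduled in the trial, and none are described for the controls.
- **Disclosure.** The plan admits that the sources differ and adds a comparison with predicted RFS for the same men. That is a partial check on case mix, but it is secondary and does not change the null in the primary test.

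**Conclusion.** The eligibility and event-free-entry mismatch is documented and makes 0.60 probably too low. The Simon rule cannot absorb even a small shift. At 0.645, the stated figure for the only series described as wholly without adjuvant therapy, its type I error is already about twice the nominal 10%. With the landmark assumption it is 0.17 to 0.28; if status is read at Day 730 on study, about 0.12 to 0.14.

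A reader might infer that the false-positive rate is established as well above 10%. The documents do not support that as a single finding. They do not give the share of the 243 men with persistent PSA (some of whom may have been detectable but below 0.2) or the share who failed before a comparable entry time. The constant first-year hazard is an assumption, and the inflation over 0.633 to 0.665 disappears under the 24-of-30 rule, at the price of power of 0.50. Nor does the MUSC comparison bear on the primary error rate; it is secondary and simply shares the same gap.

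**What to change.** 1. Re-estimate 2-year RFS in the 243-man database among men with post-operative PSA below 0.2, no adjuvant therapy, and event-free at a landmark matching the trial's surgery-to-Day-1 interval. Use the trial's event definition and follow-up time, counting death if it was recorded.
2. State which E3886 arm and n give 0.56, and use only the deferred arm.
3. State whether status is read at two years from surgery or at Day 730 on study.
4. Reset the null, keep one success rule (22 or 24), recompute the futility boundary, and restate type I error, power and detectable RFS for 30 men. As an illustration, a null of 0.65 with at least 24 of 30 gives a type I error of 0.059 and 80% power at RFS 0.84.
5. Apply the same restriction (PSA below 0.2 and event-free at entry) to the MUSC matched group.

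The cost is a re-analysis of a database the investigators have already used, a query to the ECOG statistical office that ran the E3886 analysis, and protocol wording. The downside is a less favourable detectable effect: 0.84 in the illustration, against the present 0.78.

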## 7.5 EFFICACY ASSESSMENTS

Efficacy assessments will primarily be performed by measurement of PSA and by physical assessment. Imaging studies (CT scans of the abdomen and pelvis, and bone scans) will be performed at baseline (up to 16 weeks prior to treatment) and at the end of the study (or within the preceding 2 months before end of study). Otherwise, scans will be performed only if clinically indicated for evaluation of relapse or off study. Additional forms of imaging (Prostascint scan, MRI) may be substituted for a CT scan of the abdomen and pelvis if clinically indicated. However, the imaging method used at baseline will be used for follow up scans. Compliance with therapy may be considered a component of the efficacy assessment. Compliance with PROSTVAC-V/F will be monitored at each visit by interviewing the patient and reviewing the infusion center records for administration.

Both primary and secondary efficacy assessment involve measurement of RFS. Recurrence will be defined as the occurrence of any of the following:

- Institution of new prostate cancer therapy
- First detection of a PSA level  $\geq 0.2$  ng/mL (confirmed  $> 30$  days later) after completion of all PROSTVAC V/F vaccine doses
- Development of radiographically-demonstrable metastases
- Death

RFS at two years will be met if a patient has met none of the above criteria two years post-surgery. RFS as a time to event endpoint will be measured as the time in days from surgery to any of the above conditions being met.

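### The 0.60 null lies between two control rates scored on different stated PSA rules; at the closer-matched 0.645 the 22/30 rule passes an inactive vaccine about 21% of the time, so the stated 0.10 depends on 0.60 being right

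*Combined protocol and SAP*

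**What the plan says.** The trial's PSA relapse, in section 7.5 and the synopsis, is "First detection of a PSA level" of at least 0.2 ng/mL, confirmed more than 30 days later and counted after all vaccine doses are complete. New prostate cancer therapy, radiographic metastases and death also count.

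The sample size justification in section 10.1 draws on two control sources.

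- **The 243-man database.** PSA relapse is at least 0.2 ng/mL, confirmed more than 30 days later. Result: "The observed 1yr probability of RFS was 0.751 and the 2yr probability of RFS was 0.645".
- **E3886, 98 node-positive men.** Relapse is metastasis found on imaging or examination, a PSA that first rises above 0.1 ng/mL from a nadir below 0.1 ng/mL, or death. No confirmation is stated. Result: "The observed 1yr probability of RFS was 0.73 and the 2yr probability of RFS was 0.56".

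The section acknowledges differences in disease status and in follow-up, yet holds that "the probabilities of RFS agree quite closely". It then fixes the null in these terms: "we will assume that the true probability of RFS at 2 years, for patients similar to our proposed study population, is 0.60". The target effect is an "increase in the probability of RFS from 0.6 to 0.78". Under Interim Analysis, the design stops at 11 or fewer of 19 and otherwise says "Reject the null hypothesis if there are 22 or more recurrence free among the 30 evaluable patients", with type I error 0.1 and power 0.8. The preceding paragraph of 10.1, and the synopsis, instead reject at 24 or more of 30.

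**The concern.** In a single-arm trial the null proportion is the control group. The trial counts successes under one PSA rule, while one of the two rates behind the null was, on the words of section 10.1, scored under a lower threshold with no confirmation. In the same men, such a rule can only bring relapse forward and lower RFS. The only source that shares the trial's threshold and confirmation rule gives a rate above the null being tested. If the true untreated rate is nearer 0.645 than 0.60, an inactive vaccine reaches 22 of 30 more often than the stated 10%, and a result of 22/30 supports less than the plan says it does.

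**Working it through.** **Inputs from section 10.1.** Null 0.60; alternative 0.78; stop at ≤11/19; success at ≥22/30; control rates 0.645 (n = 243) and 0.56 (n = 98).

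**Formula.** For a true 2-year RFS of p,

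P(success) = Σ over x = 12 to 19 of Bin(x; 19, p) × P[Bin(11, p) ≥ 22 − x].

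For a final cut-off of 23 or 24 the interim look changes nothing, because those totals need at least 12 or 13 successes among the first 19.

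**Step 1: reproduce the plan.** At 0.60 the result is 0.0934, and at 0.78 it is 0.8007. A search over two-stage designs returns the same minimax design. The stated 0.1 and 0.8 are therefore correct for 22/30 at a null of 0.60.

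**Step 2: control rates the plan's own sources could support.**

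- Simple mean: (0.645 + 0.56)/2 = 0.6025. The plan prints no derivation of 0.60.
- Size-weighted mean: (243 × 0.645 + 98 × 0.56)/341 = 0.621.
- Database rate with an allowance for deaths, which its definition omits. Assuming 1–2% two-year mortality: 0.645 × 0.99 = 0.639 and 0.645 × 0.98 = 0.632.

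**Step 3: probability of declaring success.**

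| True RFS | Basis | ≥22/30 (two-stage) | ≥23/30 | ≥24/30 |
|---|---|---|---|---|
| 0.60 | plan's null | 0.093 | 0.044 | 0.017 |
| 0.621 | size-weighted mean | 0.138 | 0.069 | 0.030 |
| 0.632 | database, 2% deaths | 0.167 | 0.087 | 0.039 |
| 0.639 | database, 1% deaths | 0.188 | 0.100 | 0.046 |
| 0.645 | database | 0.207 | 0.113 | 0.052 |
| 0.78 | plan's alternative | 0.801 | 0.667 | 0.499 |

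**Step 4: power if the null moves to 0.645.** The plan's effect is a ratio of 0.78/0.60 = 1.30. Applied to 0.645 this gives 0.645 × 1.30 = 0.8385, about 0.84. Power there is 0.90 for ≥23/30 and 0.80 for ≥24/30.

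**Step 5: precision of 0.645.** Treating the 243 men as a simple binomial sample (an assumption), the standard error is √(0.645 × 0.355/243) = 0.031. The 95% interval is 0.645 ± 1.96 × 0.031, about 0.585 to 0.705. Across it, the 22/30 rule passes with probability 0.07 to 0.45.

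**Step 6: how well each source matches the trial.**

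- *E3886.* Appendix B attaches the 0.1 ng/mL threshold to a different, 20-patient study. For E3886 it lists PSA progression with no threshold, and its Table 1 shows post-operative PSA ranges starting at <0.2. It also shows 47 men on immediate ADT and 51 on deferred ADT, with 5-year PFS of 83% and 27%. Section 10.1 does not say whether 0.56 pools the arms. Pooling would raise it; node-positive status would lower it against a mixed-risk cohort.
- *Database.* It admits men with persistently detectable PSA, whereas the trial requires PSA below 0.2 ng/mL, and it does not hold back PSA relapse until dosing ends. Both differences would tend to place the trial's untreated rate above 0.645. Omitting death works the other way.

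**The case against.** The strongest reply has four parts.

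1. **The plan does not say that 0.60 is an average.** This stands. The simple mean of 0.6025 fits, but the derivation is inferred.
2. **The direction of bias in 0.56 is unknown.** This stands too. A reader might infer that the PSA rule made 0.56 too low and so gave an inactive vaccine a head start. Appendix B does not support that as a finding: it gives E3886 no threshold, and immediate ADT and node status pull in opposite directions. The absence of confirmation is also only silence in the text. What remains is that 0.56 is not a like-for-like untreated rate, and that section 10.1 and Appendix B do not agree on how it was scored.
3. **0.645 is neither exact nor precise.** Its approximate interval includes 0.60. This stands, so 0.645 cannot be called the true control rate. It is still the closer match, because it shares the PSA threshold and confirmation rule and comes from men without adjuvant therapy.
4. **The plan also states a 24/30 rule, under which the error at 0.645 is 0.052.** Correct, and the synopsis gives only that rule. But 24/30 has power of about 0.50 at 0.78, not the claimed 0.80. The rule that matches the stated 0.1 and 0.8 is 22/30.

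The nomogram and matched-control comparisons among the secondary objectives give some further context, but they do not drive the success decision.

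**Conclusion.** The concern holds as a conditional statement. The type I error of 0.1 claimed for the 22/30 design is right at 0.60 and rises to 0.138 at the size-weighted mean of the plan's own sources, 0.167–0.188 at the database rate with a 1–2% allowance for deaths, and 0.207 at the database rate itself. Section 10.1 presents the two sources as close without mentioning the PSA-rule difference it has just described or the ADT received by 47 of the 98 E3886 men.

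A reader might infer that the trial's false-positive rate is 21%. The documents do not establish that. The figure assumes that the true untreated rate is 0.645 and that 22/30 is the operative rule, and the first is uncertain while the second conflicts with other text in the plan. Nor can the 0.085 gap between the sources be assigned to PSA scoring.

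**What to change.** 1. In section 10.1, qualify the statement that the rates are close by naming the PSA-rule, ADT and node-status differences. Reconcile the E3886 relapse definition there with Appendix B, and say whether 0.56 is pooled or from the deferred arm only.
2. Make the database rate the main benchmark. At minimum, pre-specify a test of the observed proportion against 0.645 beside the test against 0.60. Replace the unqualified 0.1 with the false-positive rate over nulls from 0.60 to 0.645.
3. In the same edit, choose between the 22/30 rule and the 24/30 rule in section 10.1 and the synopsis. With a null of 0.645 and 30 men, 24/30 keeps the error below 0.10 (0.052), with power 0.50 at 0.78 and 0.80 at about 0.84. A 23/30 rule gives 0.113, slightly over the limit, with power 0.67 and 0.90. State which alternative the power refers to.
4. If E3886 stays, compare it only with a sensitivity RFS in which trial PSA values are rescored on the rule stated for E3886.

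The cost is wording, restated figures and one sensitivity analysis on PSA values already collected, with no extra patients or procedures. The downside is a less favourable stated error rate or power.

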Statistics for Main Study:	
Statistical considerations:
 
Primary Objective: The primary endpoint will be a binary indicator of relapse status at the 2 year follow-up visit. Enrollment and treatment initiation must take place no more than 120 days after prostatectomy. Two-year RFS will be estimated as a proportion with an exact 95% confidence interval. RFS will also be treated as a time-to-event variable and Kaplan-Meier curves will be created; median and 95% confidence intervals will be reported.
 
The data from this trial will be compared with results from historical control data obtained from a multi-institutional database which includes high-risk, post-prostatectomy subjects without adjuvant therapy (n = 243), and from a published clinical trial (n = 98). The estimated 2-year probability of RFS of high-risk subjects after prostatectomy is 0.6. We define an "interesting" improvement in RFS to be 30% (i.e. increase in the probability of RFS from 0.6 to 0.78). Assuming a one-sided alpha = 0.1, with 30 patients in a group, we have 80% power to detect this difference based on an exact binomial test. Thus if among 30 evaluable subjects, at least 24 are recurrence free at 24 months, we will reject the null hypothesis (2-year RFS=0.60) and conclude that the PROSTVAC intervention improves RFS relative to the RFS of similar patients receiving no adjuvant therapy.
 
Secondary objectives: a) A secondary objective will be a comparison of observed RFS times with the predicted RFS times for the treatment cohort using the Duke and CaPSURE nomograms. The comparison will be performed using the logrank test of the observed and predicted RFSs.
 
b) Biochemical and genomic measurements will be graphically displayed to evaluate their distributions. Transformations will be taken as appropriate. Cox regression will be used to estimate hazard ratios measuring the association between these measures and RFS. 95% confidence will be estimated for the hazard ratios as appropriate.
 
c) Toxicities will be tabulated by CTCAE grade and type.

-----------------------------------	--

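### The success threshold is given as both 24 of 30 and 22 of 30. Only 22 gives the stated alpha of 0.10 and 80% power, and the 30% relapse-risk reduction in section 10.1 is really 45%.

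*Combined protocol and SAP*

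**What the plan says.** The planning assumptions are the same wherever they appear: null 2-year RFS 0.60, alternative 0.78, an exact binomial test, 30 evaluable patients. Section 10.1, Sample Size Justification, sets the level with "Assuming a one-sided alpha = 0.1, with 30 evaluable patients" and adds that "we have 80% power to detect this difference based on an exact binomial test".

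The next sentence draws the decision rule from this: "Thus if among 30 evaluable subjects, at least 24 are recurrence free at 24 months, we will reject the null hypothesis". It attaches a one-sided p-value of at most 0.025. The synopsis (Statistics for Main Study) repeats the 24-of-30 rule beside alpha 0.1 and 80% power, without the p-value bound.

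A few lines later, the Interim Analysis text of section 10.1 describes a Simon minimax two-stage design. The first stage is "Stop the study if there are 11 or fewer recurrence free among the first 19 evaluable patients". The final rule is "Reject the null hypothesis if there are 22 or more recurrence free among the 30 evaluable patients". A type I error of 0.1 and power of 0.8 are claimed for this design.

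The target effect is also worded in two ways. Section 10.1 calls it a "reduction in the risk of relapse to be 30% (i.e., increase in the probability of RFS from 0.6 to 0.78"); the synopsis calls it an "improvement in RFS to be 30% (i.e. increase in the probability of RFS from 0.6 to 0.78").

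**The concern.** A single-arm, open-label trial judged against a historical rate depends on one success threshold fixed in advance. Here there are two, for the same null, patients and endpoint, and nothing says which governs. A result of 22 or 23 of 30 would be positive under the Simon rule and negative under the synopsis and the sample-size paragraph, so the choice could be made after the data are known.

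The sample-size paragraph presents the 24 threshold as following from alpha 0.10 and 80% power, then attaches a p-value bound four times stricter than that alpha. Both the power claim and the threshold cannot be right. A reader of the synopsis alone would take the 24 rule to have 80% power.

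The effect wording matters less, but it could lead a reader of section 10.1 to think the trial has 80% power for a smaller benefit than the one it was sized for.

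**Working it through.** **Inputs** (section 10.1): p0 = 0.60, p1 = 0.78, n = 30 evaluable, one-sided alpha 0.10, power 0.80; stop at 11 or fewer of 19; final threshold r = 24 or r = 22.

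**Formula.** For a rule that rejects at r or more successes, P(X ≥ r | p) = Σ (x = r to 30) C(30, x) pˣ (1 − p)³⁰⁻ˣ. Alpha is this sum at p = 0.60; power is the sum at p = 0.78.

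**Single-stage results, n = 30**

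| Reject at | Alpha (p = 0.60) | Power (p = 0.78) |
|---|---|---|
| ≥ 21 | 0.1763 | 0.8961 |
| ≥ 22 | 0.0940 | 0.8025 |
| ≥ 23 | 0.0435 | 0.6667 |
| ≥ 24 | 0.0172 | 0.4992 |

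The plan's own figures are reproduced at 22: the smallest threshold that keeps alpha at or below 0.10 is 22, and its power is 0.8025. At 24, power is 0.4992.

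**With the interim stop.** Sum over first-stage counts x₁ = 12 to 19: P(X₁ = x₁) × P(X₂ ≥ r − x₁), where X₂ is the count in the remaining 11 patients.

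- r = 22: alpha 0.0934, power 0.8007.
- r = 24: alpha 0.0172, power 0.4992, unchanged. A trial stopped at 11 of 19 could have reached at most 11 + 11 = 22, so the stop never removes a path to 24.

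An exhaustive search for the minimax design with alpha ≤ 0.10 and power ≥ 0.80 returns 11/19 followed by ≥ 22 of 30, with 30 the smallest feasible total. The Simon paragraph is therefore correct as printed.

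**How often the rules disagree.** P(X = 22 or 23) = P(X ≥ 22) − P(X ≥ 24).

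- At 0.78: 0.8025 − 0.4992 = 0.303.
- At 0.60: 0.0940 − 0.0172 = 0.077.

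**The p-value bound.** The exact one-sided p-value is 0.0172 at 24 of 30 and 0.0435 at 23 of 30, so 24 is the critical value for a one-sided level of 0.025. At that level, the smallest n with 80% power at 0.78 is 54 (≥ 40 of 54: alpha 0.0222, power 0.8076).

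**The effect size.**

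- Relative gain in RFS: 0.78 / 0.60 − 1 = 0.30.
- Relative reduction in relapse risk: 1 − 0.22 / 0.40 = 0.45.
- A true 30% reduction in relapse risk means risk 0.40 × 0.70 = 0.28, so RFS 0.72. Power there is 0.528 at ≥ 22 (0.526 two-stage) and 0.224 at ≥ 24.

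**Interval beside the test.** The planned exact 95% interval has lower limit 0.541 at 22 of 30, 0.577 at 23 and 0.614 at 24. Under the 22 rule, a positive result at 22 or 23 would be shown with an interval that still includes 0.60. The one-sided 90% lower limit at 22 of 30, computed as single-stage, is 0.603.

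**The case against.** The strongest reply is that the design is sound and only a stray threshold is at fault. The 22 rule is explicitly labelled as the decision rule at 30 evaluable patients, and it alone matches the stated alpha, power, sample size and interim boundary, so a careful reader could work out which number was meant. That is fair, and it is why the repair is small. It does not remove the problem: the 24 rule is equally explicit, stands in two places including the synopsis, and no text ranks one above the other.

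Second, an alpha of 0.017 does not breach a ceiling of 0.10, and 24 of 30 agrees with the 0.025 bound in its own sentence. Both points stand. The failed claim for the 24 rule is therefore its power, and its level is far stricter than the one used for sizing.

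Third, the two rules disagree in a minority of outcomes: 0.303 at the design alternative and 0.077 under the null. This also stands. A 30% chance of an ambiguous result if the vaccine works as hoped is still too large to leave open.

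Fourth, section 10.1 gives 0.6 and 0.78 numerically, so the power refers to that difference and the 30% phrase is a slip in one place. Agreed: it is secondary, and power at RFS 0.72 illustrates its effect without being a required analysis. Likewise, a two-sided 95% interval used for estimation need not agree with a one-sided 0.10 test.

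**Conclusion.** The concern holds. Two incompatible success thresholds are in force for the primary endpoint. The stated one-sided alpha of 0.10 and 80% power belong only to 22 of 30 (0.094 and 0.802 single-stage; 0.093 and 0.801 with the 11-of-19 stop). The 24-of-30 rule has alpha 0.017 and power 0.50. The effect described in section 10.1 as a 30% reduction in relapse risk is a 45% reduction.

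These figures assume exactly 30 evaluable patients, each with a known binary status at two years, and the plan's own rates of 0.60 and 0.78. They do not depend on any outside figure. Neither the sample size of 30 nor the futility rule is in error. That the 24 threshold came from a 0.025 critical value is an inference from the p-value bound beside it; the protocol does not say so.

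This must be corrected before the primary outcome is analysed, because it decides whether a plausible result counts as success.

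**What to change.** State one success rule and use it everywhere.

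- **If one-sided alpha 0.10 and 80% power are intended:** in the synopsis and the Sample Size Justification, replace 24 by 22. Delete the p-value bound of 0.025. Keep the nominal one-sided level of 0.10 and report the attained two-stage values (type I error 0.093, power 0.801). Do not turn 0.093 into a p-value cut-off: the exact p-value at 22 of 30 is slightly above it.
- **If a one-sided level of 0.025 was intended:** restate the power with 30 patients as about 50%, or resize to about 54 evaluable patients for 80% power, and rederive the two-stage boundaries.
- **Effect wording in section 10.1:** describe the target as a 30% relative increase in 2-year RFS (0.60 to 0.78), equivalent to a 45% relative reduction in relapse risk (0.40 to 0.22).
- **Optional:** report the one-sided 90% lower limit beside the exact 95% interval, so that a positive result at 22 or 23 is not shown only with an interval that includes 0.60.
- **In the same amendment:** reconcile section 4.1, which still gives 40 evaluable subjects (44 in total) against 30 (33) elsewhere. Neither threshold is defined for 40.

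The first option costs only protocol text: no added patients, visits or data. The second costs either the power claim or about 24 more evaluable patients (54 − 30).
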